3.5.2 Missing data imputation

For AE data, missing causality will be imputed to “Related” and missing intensity grade will be imputed to “Grade 3 – Severe”.

Other missing data will not be imputed unless other specified.

3.5.3 Lab values below or above a threshold

Lab results below or above a threshold, e.g. " \geq 50 mg/dL, will be excluded from descriptive statistics. The number of patients with results below or above the threshold will be presented for each lab parameter.

3.6 Interim Analyses

No interim analysis was planned for Part B of the study.

3.7 Handling of Study Center Effects

Study center effects will not be assessed.

3.8 Documentation & Other Considerations

Data are entered electronically into a clinical database built by Medidata RAVE and exported as SAS® datasets. SDTM and ADaM datasets will be generated following the Clinical Data Interchange Standards consortium (CDISC) conventions (SDTMIG v3.2 and ADaMIG v1.1). Summary tables and figures will be produced based on the ADaM datasets and patient data listings will be produced based on the SDTM datasets or raw clinical database. All tables, figures and listings will be produced using SAS® version 9.4.

AEs are coded using the Medical Dictionary for Regulatory Activities (MedDRA) Version 18.0, to assign a system organ class (SOC) and preferred term (PT) to each AE. Prior and concomitant medications are coded to preferred drug names using the World Health Organization Drug Dictionary (WHODRUG) dictionary WHO-DDE-B2-June 2015.

Continuous data will be summarized with the following descriptive statistics unless otherwise noted: number of observations, mean, standard deviation (SD), median, minimum, and maximum. Categorical data will be summarized with frequencies and percentages. Patient data listings will be listed patient ID and visit, unscheduled visits will be placed in chronological order.

No hypothesis testing will be performed.

For presentation of data, the mean and median will be presented to 1 decimal place greater than the original data, SD will be to 2 decimal places greater than the original data, and the minimum and maximum will have the same number of decimal places as the original data. Change from screening and change from baseline will be 1 decimal place greater than the observed statistics. The format for minimum and maximum will be "Min, Max". Standard deviation will be abbreviated as "SD". Percentage will be reported to 1 decimal place.

For the shift tables, the Normal to Abnormal or Normal to Out-of-Range shifts will be highlighted in yellow. Zero (0) count and percentage will not be displayed.

For the abnormal results listings, the abnormal or out-of-range results will be highlighted in yellow and clinically significant values will be in highlighted in a different color with bold font.

4 STATISTICAL METHODS

4.1 Safety Endpoints

The incidence of treatment-emergent AEs (TEAEs), including clinically significant changes in physical examination, laboratory tests, and vital signs.

4.2 Primary Efficacy Endpoint

The primary efficacy endpoint is the proportion of patients who are able to achieve control of disease activity (CDA) within 4 weeks of starting PRN1008 treatment without the need for doses of prednis(ol)one >0.5 mg/kg on or before the Week 5 visit.

CDA is defined as the time at which new lesions cease to form and established lesions begin to heal.

4.3 Secondary Efficacy Endpoints

The secondary efficacy endpoints are:

- 1) Cumulative incidence of patients able to achieve CDA by each visit
- 2) Cumulative incidence of patients able to achieve CDA by each visit on zero steroids.
- 3) Cumulative incidence of patients able to achieve CDA by each visit **with** the need for doses of prednis(ol)one of greater than 0.5 mg/kg
- 4) Cumulative incidence of patients able to achieve CDA by each visit **without** the need for doses of prednis(ol)one of greater than 0.5 mg/kg
- 5) Proportion of patients able to achieve CDA at each visit
- 6) Proportion of patients able to achieve CDA at each visit **with** the need for doses of prednis(ol)one of greater than 0.5 mg/kg
- 7) Proportion of patients able to achieve CDA at each visit **without** the need for doses of prednis(ol)one of greater than 0.5 mg/kg
- 8) Cumulative incidence of patients able to achieve CR by each visit
- 9) Cumulative incidence of patients able to achieve CR by each visit **with** the need for doses of prednis(ol)one of greater than 0.5 mg/kg
- 10) Cumulative incidence of patients able to achieve CR by each visit **without** the need for doses of prednis(ol)one of greater than 0.5 mg/kg
- 11) Proportion of patients able to achieve CR at each visit
- 12) Proportion of patients able to achieve CR at each visit **with** the need for doses of prednis(ol)one of greater than 0.5 mg/kg
- 13) Proportion of patients able to achieve CR at each visit **without** the need for doses of prednis(ol)one of greater than 0.5 mg/kg
- 14) Proportion of patients able to achieve a complete CR **with** the need for dose of prednis(ol)one of greater than 0.5 mg/kg within 24 weeks, i.e. on or prior to Week 25 visit
- 15) Proportion of patients able to achieve a complete response (CR) **without** prednis(ol)one of greater than 0.5 mg/kg within 24 weeks, i.e. on or prior to Week 25 visit

- 16) Time to first CDA
- 17) Time to first CR
- 18) Time to first end of consolidation phase
- 19) Time to first relapse (after CDA has been achieved, as per relapse definition)
- 20) Time to first increase in PDAI
- 21) Cumulative CS usage over 24 weeks
- 22) Change from baseline in Pemphigus Disease Area Index (PDAI) and Autoimmune Bullous Skin Disorder Intensity Score (ABSIS) scores at each visit
- 23) Change from baseline in Autoimmune Bullous Diseases Quality of Life (ABQOL) and Treatment of Autoimmune Bullous Diseases Quality of Life (TABQOL) scores at each visit
- 24) Change from baseline in appetite (SNAQ score) at each visit

CR, End of consolidation phase, and Relapse definitions are listed below and noted where they differ listed below:

- Complete response (CR): the absence of new or established lesions while the patient is receiving low dose CS, defined in this study as $< \text{ or } = 0.5\text{mg/kg}$ or 0, as stated in the specific endpoint. The duration of CR is not part of the definition for this study.
- End of consolidation phase: The time at which no new lesions have developed for minimum of 2 weeks, approximately 80% of lesions have healed, and when most clinicians start to taper steroids.
- Relapse/flare: Appearance of ≥ 3 new lesions/month that do not heal spontaneously within 1 week, or by extension of established lesions, in a patient who has achieved disease control

4.4 Pharmacokinetic Outcome Measure

Plasma concentrations of PRN1008 will be measured at approximately the time of maximum concentration on Day 1 and at various subsequent times during outpatient dosing.

A separate SAP will describe the PK outcome measures and analyses. PK results will be summarized in an independent report.

4.5 Pharmacodynamic Outcome Measures

- Percentage BTK occupancy for individuals in PBMCs will be determined at 2 & 24 hours after the first PRN1008 dose and at varied subsequent times during outpatient dosing
- Actual result, change and percent change from screening and change and percent change from baseline in Anti-DSG-1-3 autoantibody levels by ELISA at various time points for all patients and by baseline Anti-DSG-1-3 values of ≥ 100 unit vs. < 100 unit.

A separate SAP will be created for the BTK occupancy analysis and the results will be summarized in a separate report.

4.6 Exploratory Measures

- Exploratory PK/PD analysis will examine the effects, if any, of covariates on PK and/or PD, and the relationship between PK, PD and efficacy in this population

A separate SAP will be created for the PK/PD analysis and the results will be summarized in a separate report.

4.7 Changes to Planned Analyses from Protocol

Change	Description	See SAP section
Analysis populations	The following analysis populations are added: 
 ▪ Modified Intent-to-Treat (mITT) Population ▪ Completer Population ▪ Per-Protocol (PP) Population 	3.2.4, 3.2.5, 3.2.6
Secondary endpoints	The secondary endpoints are re-ordered to group all the CDA endpoints together and then followed by the CR endpoints. Some of the endpoints are re-worded for clarity and consistency within the SAP but the meaning and interpretation remained the same as defined in the protocol.	4.3, 5.4.2.1
Additional secondary endpoints	The following secondary efficacy endpoints were not listed in the protocol but included in the Part A SAP. They will be also analyzed for Part B of the study. 
 • Proportion of patients able to achieve CDA at each visit • Proportion of patients able to achieve CDA at each visit with or without the need for doses of prednis(ol)one of greater than 0.5 mg/kg • Cumulative incidence of patients ever achieved CDA by each visit • Cumulative incidence of patients able to achieve CDA by each visit on zero steroids. • Cumulative incidence of patients ever achieved CDA by each visit with or without the need for doses of prednis(ol)one of greater than 0.5 mg/kg • Proportion of patients able to achieve CR at each visit • Proportion of patients able to achieve CR at each visit with or without the need for doses of prednis(ol)one of greater than 0.5 mg/kg • Cumulative incidence of patients ever achieved CR by each visit 	4.3

	
• Cumulative incidence of patients ever achieved CR by each visit with or without the need for doses of prednis(ol)one of greater than 0.5 mg/kg• Time to first increase in PDAI	
--	---	--

5 ANALYSIS DETAILS

5.1 Patient Disposition, Demographics and Baseline Characteristics

The Screening population will be used for patient disposition and reason for screen fails. The ITT population will be used for demographics and baseline characteristics. Descriptive statistics will be done by starting dose and overall, unless specified otherwise. Patient data listings will be listed by starting dose and patient and start date of event, if applicable.

5.1.1 Patient Disposition

The number and percentage of patients will be tabulated for patients who:

- Enrolled into the study (Screening population)
- Had at least one dose of PRN1008 (Safety and ITT populations)
- Completed treatment up to Week 5 and had a Week 5 disease assessment (mITT population)
- Had no major protocol deviations, completed Week 29/Day 197 visit and had at least 80% study drug compliance (PP population)
- Completed the study
- Early discontinued
- Reason for early discontinuation for patients who early discontinued
 - Adverse Event
 - Death
 - Lack of Efficacy
 - Lost to Follow-up
 - Non-Compliance with Study Drug
 - Physician Decision
 - Pregnancy
 - Progressive Disease
 - Recovery
 - Trial Screen Failure
 - Study Terminated by Sponsor
 - Technical Problem
 - Withdrawal by Subject
 - Other

The number and percentage of patients who attended each visit and the number of percentages of patients enrolled by country and study site will also be tabulated.

Detailed disposition, study enrollment and analysis population information will be listed.

Screen failures will be listed with date and reason for screen failure.

5.1.2 Demographics and Baseline Characteristics

Demographics variables including age, gender, fertility status and method of birth control for female patients, race, ethnicity, height at screening (cm), weight at screening (kg) and body mass index (BMI) (kg/m^2) at screening will be summarized by descriptive statistics and listed in a patient data listing.

5.1.3 Disease History

Disease history data including pemphigus subtype at screening, time from pemphigus diagnosis (by the earliest medical history record) date to screen date (years), Pemphigus history type (Newly diagnosed vs. Relapsed), baseline Anti-DSG 1 and Anti-DSG 3 antibody status/profile, Total Anti-DSG at baseline (< 100 vs ≥ 100) PDAI total activity score, Pemphigus severity at baseline (PDAI < 15 (mild-moderate) or PDAI ≥ 15 (moderate-severe)), PDAI mucous membrane activity ($\% > 0$), PDAI scalp activity ($\% > 0$), PDAI skin activity ($\% > 0$) and ABSIS oral activity ($\% > 0$) will be summarized in a frequency table and listed.

Newly diagnosed pemphigus is defined as subjects who were diagnosed at most 180 days prior to date of screening, otherwise the patient is defined as relapsed.

Baseline Anti-DSG status will be determined by the central lab results and presented in the following categories:

- Anti-DSG 1 positive, Anti-DSG 3 negative;
- Anti-DSG 1 negative, Anti-DSG 3 positive;
- Anti-DSG 1 positive, Anti-DSG 3 positive;
- Anti-DSG 1 negative, Anti-DSG 3 negative

Ranges for Anti-DSG status:

	Status	Range
Anti-DSG 1	positive	≥ 14
	negative	< 14
Anti-DSG 3	positive	≥ 9
	negative	< 9

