6 STUDY POPULATION

The study population is male or female patients with newly diagnosed (i.e., naïve to an effective induction treatment regimen) or relapsing, biopsy-proven, mild to severe PV (PDAI 8-60), for whom an initial period of PRN1008 monotherapy is judged clinically acceptable.

Because patients without mucosal involvement but with a medical history suggestive of PV are allowed into the study, some patients with clinical features suggestive of the pemphigus foliaceus (PF) variant of the disease may be enrolled.

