7 LIST OF SCREENING ASSESSMENTS

The Schedule of Assessments is presented in [Appendix 4](#). All participants must sign and date the most current Institutional Review Board (IRB)-approved written informed consent form before any study specific assessments or procedures are performed. An original signed consent form will be retained by the Investigator and the participant will be given a copy of the signed consent form.

Participants must fulfill all entry criteria to be enrolled into the study. Participants who fail to meet the entry criteria may be rescreened once at the discretion of the Investigator. A record of eligibility screening documenting the Investigator's assessment of each screened participant with regard to the protocol's inclusion and exclusion criteria, including screen failures, is to be completed and signed by the Investigator or designee. Ethnicity of participants will be recorded, since this information might be important to evaluate a potential impact of ethnic factors on drug properties [see also ICH Guideline E5 (R1)].

Up to 28 days before enrollment in the study, participants will be required to sign a consent form, after which screening assessments will be carried out. After providing written informed consent, subjects will complete the Screening Assessments within 28 days before the first dose of PRN1008:

- Review of medical history and concomitant medication
- PDAI, ABSIS assessments
- Review of inclusion and exclusion criteria
- Measurement of height and weight
- Physical examination
- 12-Lead ECG
- Vital signs (blood pressure, heart rate, respiration rate, and temperature)
- Clinical laboratory testing (hematology, coagulation, serum chemistry, and urinalysis)
- HIV, hepatitis B (surface antigen and core antigen and antibodies), hepatitis C (anti-HCV antibody confirmed with Hep C RNA)
- TB screen with T-spot TB Test, QuantiFERON®-TB Gold, or QuantiFERON®-TB Gold Plus (QFT Plus)
- Serum pregnancy test for females of child bearing potential
- FSH (in postmenopausal women who are not surgically sterile only)
- Skin biopsy if not already performed: lesional for H&E staining, perilesional for direct immunofluorescence

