6.1. Demographics

A summary of demographics and baseline characteristics will be presented overall and by maximum dose level for the Safety Analysis Population/ITT Population, mITT Population and PP Analysis Population. The demographic characteristics consist of age (years), sex, race, and ethnicity. The baseline characteristics consist of baseline pemphigus (clinical diagnosis) type, time from pemphigus vulgaris confirmed date to screen date (Months), baseline Anti-DSG 1 and Anti-DSG 3 antibody status/profile, baseline height (cm), baseline weight (kg), baseline body mass index (BMI) (kg/m^2), PDAI total activity score, PDAI mucous membrane activity ($\% >0$), PDAI scalp activity ($\% >0$), PDAI skin activity ($\% >0$), ABSIS oral activity ($\% >0$), and CS dose on screening date and Week 1 Day 1 date, which is summarized in the CS summary table separate from the demographics summary.

A patient's age in years is calculated using the date of the informed consent and date of birth. Age, height, weight, BMI, PDAI total activity score, and CS Dose on the day of screening and Week 1 Day 1 will be summarized using descriptive statistics. The number and percentage of patients by sex (Male, Female), race (White, Black or African American, Asian, American Indian or Alaska Native, Native Hawaiian or Other Pacific Islander, and Other), ethnicity (Hispanic or Latino, Not Hispanic or Latino), baseline pemphigus type (Pemphigus Vulgaris, Bullous Pemphigoid, Pemphigus Foliaceus, Epidermolysis Bullosa Aquisita, Linear IgA Bullous Dermatoses, Mucous Membrane Pemphigoid, and Other). Time from pemphigus vulgaris confirmed date to screen date in months is defined as $(\text{Date of Screening} - \text{Date of pemphigus vulgaris confirmed} + 1) / 30.4375$.

Baseline Anti-DSG status will be presented in the following categories, using the limits of detection as the basis for positive/negative determination:

- Anti-DSG 1 positive, Anti-DSG 3 negative;
- Anti-DSG 1 negative, Anti-DSG 3 positive;
- Anti-DSG 1 positive, Anti-DSG 3 positive;
- Anti-DSG 1 negative, Anti-DSG 3 negative;

No formal statistical analyses will be performed, and no inferential statistics reported.

Subgroup analyses variables detailed in Section 8.2.11 will also be summarized by categories.

Patient demographic and baseline characteristics will be presented in a listing for the Safety Analysis Population.

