8.2.11. Subgroup Analysis

The rates of the primary endpoint will be calculated in selected subgroups:

1. Age (≥ 50 , < 50)
2. Gender
3. Total anti-desmoglein (dsg) antibody (≥ 100 , < 100 units) at baseline.
4. Pemphigus History Type: Newly diagnosed (≤ 6 months from screening) vs. relapsed (> 6 months)
5. Pemphigus Anti-DSG Profile at baseline: PV vs. PF vs. negative anti-dsg profile, where PV is defined as anti-dsg3 positive with anti-dsg1 negative or anti-dsg 3 positive with anti-dsg1 positive. PF=anti-dsg1 positive only vs. neither detectable).
6. Pemphigus Severity: Mild vs. moderate disease severity at baseline (PDAI total activity < 15 vs. ≥ 15). If screening PDAI is not available use Day 1.

9. Safety Analysis

Specific assessments to evaluate treatment safety include the following: the frequency and type of adverse events, clinical laboratory testing, brain MRI (baseline and Day 15 in a subset of patients), vital signs, and symptoms and/or signs of headache, nausea, vomiting or visual disturbances. All analyses of safety will be conducted using the Safety Analysis Population.

For by visit summaries, unscheduled visits, if they exist in the data, will be presented separately after other visits.

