3.4.6 Time from Pemphigus Diagnosis (years)

Time from event (years) = (Date of screening – First date of Pemphigus reported in Medical History + 1)/365.25

3.4.7 Control of Disease Activity (CDA), Complete Remission (CR), End of Consolidation Phase (ECP) and Relapse

Control of Disease Activity (CDA) is defined as the time at which new lesions cease to form and established lesions begin to heal. This is also considered the beginning of the consolidation phase. Date of CDA should be the first date CDA occurred i.e. a visit date or earlier date reported by the patient. If there is a relapse and a subsequent second CDA, visits from that second CDA visit forward would record the date of the second CDA. If CDA is yes, relapse must be no.

Complete remission (CR) in this study is defined as the complete healing of all lesions and absence of new lesions on any dose of corticosteroid or no steroids. Date of CR should be the first date CR occurred i.e. a visit date or earlier date reported by the patient. The duration of time in CR e.g. 8 weeks is not included in the definition. If CR is yes, CDA, ECP must be yes also, and relapse must be no.

End of Consolidation Phase (ECP) is defined as the time at which no new lesions have developed for a minimum of 2 weeks and the majority (approximately 80%) of established lesions have healed. It is at this point that most clinicians begin to taper corticosteroid doses. Date of ECP should be the first date ECP occurred i.e. a visit date or earlier date reported by the patient. If ECP is yes, CDA must be yes also, and relapse must be no.

Relapse (i.e. flare) is defined by the appearance of 3 or more new lesions in a month that do not heal spontaneously within 1 week, or by the extension of established lesions, in a patient who has achieved control of disease (i.e. CDA). Date of relapse should be the first date relapse occurred i.e. a visit date or earlier date reported by the patient. If relapse is yes, CDA, ECP and CR must be no.

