3.5 Data Handling

3.5.1 Partial dates

Imputation of day, month and/or year for partial or missing AE onset dates will be performed as described below.

- Day, month and year missing
 - Leave as missing, no imputation. In this case, the adverse event will be considered as treatment emergent.
- Day and month missing
 - If year of start date is the same as the year of the 1st dose of PRN1008, then impute day and month as the day and month of 1st dose of PRN1008, ELSE
 - Impute day and month as 31-DEC, if the year is before the year of the 1st dose of PRN1008, ELSE

- Impute day and month as 01-JAN, if the year is after the year of the 1st dose of PRN1008
- Only day missing
 - If the year is the same as the year of the 1st dose of PRN1008
 - If the month is before the month of the 1st dose of PRN1008, then the last day of the month will be assigned to the missing day.
 - If the month is the same as the month of the 1st dose of PRN1008, then the day of the 1st dose of PRN1008 will be assigned to the missing day.
 - If the month is after the month of the 1st dose of PRN1008, then “01” will be assigned to the missing day.
 - If the year is before the year of the first dose of study drug, then the last day of the month will be assigned to the missing day.
 - If the year is after the year of the first dose of study drug, then “01” will be assigned to the missing day.

Imputation of day, month and/or year for partial or missing medication stop dates will be performed as described below if the medication is not flagged as “Ongoing”.

- Day, month and year missing
 - Leave as missing, no imputation. In this case, the medication will be considered as concomitant.
- Day and month missing
 - If year of stop date is the same as the year of the 1st dose of PRN1008, then impute day and month as the day and month of 1st dose of PRN1008, ELSE
 - Impute day and month as 31-DEC.
- Only day missing
 - If month and year of start date are prior to the month and year of the 1st dose of PRN1008, then impute day as 01, ELSE
 - Impute day as day of 1st dose of PRN1008.

Imputation of day and month for partial Date of PV Diagnosis (years) will be performed as described below.

- If only day is missing, impute as 01
- If day and month are missing, impute as 01-JAN

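### Both SAPs label patients 'newly diagnosed' or 'relapsed' from time since diagnosis alone, while the protocol and the SAPs' own design sections define newly diagnosed by prior induction treatment

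*SAP*

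**What the plan says.** Protocol section 6 describes the population as "newly diagnosed (i.e., naïve to an effective induction treatment regimen) or relapsing". That is a statement about treatment history, with no time limit. The Part A SAP (3.1) and the Part B SAP (2.2) repeat it in their design sections.

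The analysis sections use a different rule:

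- **Part A SAP 8.2.11, item 4**, headed "Pemphigus History Type: Newly diagnosed", splits at 6 months before screening. Footnote [2] of Table 14.1.2.1 assigns everyone outside that window to relapsed.
- **Part B SAP 5.1.3** defines newly diagnosed as "subjects who were diagnosed at most 180 days prior to date of screening, otherwise the patient is defined as relapsed".
- **Part B SAP 5.4.1.1, item 4**, the subset analysis of the primary endpoint, uses 6 months.

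Part B SAP 3.4.6 measures time since diagnosis from the "First date of Pemphigus reported in Medical History". For partial diagnosis dates, Part B SAP 3.5.1 says: "If day and month are missing, impute as 01-JAN".

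The primary-endpoint response is tabulated by these groups in Tables 14.2.10.4.1–3 (Part A) and B.14.2.1.5.1–3 (Part B), each in three populations. Neither section on changes to the planned analysis (Part A SAP 13, Part B SAP 4.7) mentions the different definition.

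**The concern.** A reader of these tables will take 'relapsed' to mean that the disease came back after control. Both SAPs use the word that way for on-study outcomes: relapse there requires a patient who has already achieved disease control (Part A SAP 3.2.3, Part B SAP 3.4.7). At baseline, nothing about control, relapse or earlier treatment enters the rule. Its only inputs are a diagnosis date and the screening date, so patients can be placed wrongly in either direction.

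The protocol says the results will be used to design confirmatory trials. A response rate headed 'relapsed' that includes patients never shown to have relapsed is a poor basis for choosing or stratifying that population. Mixing the two groups also tends to pull their rates together, so a real difference can look smaller than it is.

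**Working it through.** **1. Definition against rule.** Four cases suffice.

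| Patient | Protocol section 6 | SAP label |
|---|---|---|
| Never induced, diagnosed 3 months ago | newly diagnosed | newly diagnosed |
| Never induced, diagnosed 8 months ago | newly diagnosed | relapsed |
| Induced, relapsed, diagnosed 5 months ago | relapsing | newly diagnosed |
| Induced, relapsed, diagnosed 3 years ago | relapsing | relapsed |

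The two middle rows are misplaced. The documents do not give the joint distribution of time since diagnosis and treatment history, so the number of such patients cannot be computed.

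**2. The plan's own precision.** For 25 patients per Part and a 50% response, the 80% half-width is 1.2816 × √(0.5 × 0.5 / 25) = 0.128, which reproduces the stated ±13%. A subgroup is roughly half that size. With an assumed 6 responders of 12, the exact 80% interval is 28.8% to 71.2% and the exact 95% interval 21.1% to 78.9%.

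**3. Dilution (assumed values).** Let true rates be 70% in uninduced and 40% in relapsing patients, and let a share q of each labelled group belong to the other. The observed difference is 30 × (1 − 2q) points:

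| q | 0 | 10% | 20% | 30% | 40% | 50% |
|---|---|---|---|---|---|---|
| Difference (points) | 30 | 24 | 18 | 12 | 6 | 0 |

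Here q is the share of each *labelled* group. If m is instead a common error rate in each *true* group, the factor 1 − 2m requires equal group sizes. With a 30/70 split and m = 20%, the true newly diagnosed make up 0.24/0.38 = 63.2% of one labelled group and 0.06/0.62 = 9.7% of the other. A 40-point difference then shows as 40 × (0.632 − 0.097) = 21 points, against 24 with equal groups.

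**4. Part B is not a single time rule.**

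- *Cut-off.* 5.1.3 and Table B.14.1.3.1 use 180 days. 5.4.1.1, Table B.14.2.1.5.x and Listing B.16.2.1.6 use 6 months. At the Part A SAP's 30.4375 days per month, 6 months is 182.6 days, so a patient at 181 days changes group between tables.
- *Date.* 3.4.6, 5.1.3 and Table B.14.1.3.1 use the earliest medical-history record. Listing B.16.2.1.6 shows the date PV was confirmed, and time from it, beside the same label.
- *Severity.* The footnote to Table B.14.2.1.7.x gives mild as 0–14 and moderate as 15–44 for newly diagnosed patients, but mild as 0–8 and moderate as 9–24 for relapsed patients. A PDAI of 9–14 is therefore mild or moderate depending only on this label. 5.4.1.1 item 6 has a single cut at 15.

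Part A has a smaller slip of the same kind: the footnote for Table 14.2.10.4.x excludes exactly 6 months, while 8.2.11 and Table 14.1.2.1 include it.

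**5. The 01-JAN rule.** I take the rule in 3.5.1 to feed this classification. Assume screening day S is uniform over 365 days, true interval T is uniform over 0–180 days, and only the year of diagnosis is known.

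- If T > S, the diagnosis year is the previous one, the imputed interval is S + 365, and the label is relapsed.
- If T ≤ S, the imputed interval is S, and the patient stays newly diagnosed only if S ≤ 180.

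The chance of a correct label is the integral of (s/180)/365 for s from 0 to 180, which is 90/365 = 24.7%. So 75.3% of such patients would be labelled relapsed. This applies only to recent diagnoses recorded by year alone, and the documents do not say whether any exist.

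**The case against.** The best reply is that this is mostly a labelling matter. Section 6 of the protocol describes who may enrol; the protocol plans no such subgroup (11.5.3 and 11.9.1 give disease severity and dose group only as examples) and has no baseline definition of relapsing or of an effective regimen. The 6-month limit is printed with the groups in several places. The subgroup is one of six, descriptive, with about 25 patients per Part, and Part B performs no hypothesis testing. A date rule is also objective, whereas judging past induction after outcomes are known, in an open-label study, is not.

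Much of this stands, and it limits both the weight of the point and the remedy. It does not remove the conflict: each SAP gives one meaning in its design section and applies another in its tables, without saying so.

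Some stronger readings are not supported:

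- **Part A dates diagnosis from a screening biopsy, making long-standing disease look new.** Part A SAP 6.1 does set out "Time from pemphigus vulgaris confirmed date to screen date in months is defined as" a formula, and the protocol's screening list includes "Skin biopsy if not already performed". But the subgroup rule and its footnotes refer only to diagnosis and do not name the PV-confirmed date. The biopsy is also taken only when no suitable earlier one exists.
- **The Parts cannot be pooled for this subgroup.** The protocol allows combining where appropriate, but neither SAP plans to pool this split.
- **The correct status is already on file from Inclusion 2.** That criterion admits either type; nothing shows which one was recorded. Medications are captured only from 28 days before screening (protocol 16.12).

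**Conclusion.** The point holds as a conflict of definition. Both SAPs report primary-endpoint rates for patients called 'relapsed' who need not have relapsed, and for patients called 'newly diagnosed' who may have been induced and relapsed. Part B adds inconsistent cut-offs, an inconsistent displayed date, a severity footnote that depends on the label, and an imputation rule that can only move a year-only diagnosis earlier, towards 'relapsed'.

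The size is unknown. A reader might infer that the reported rates are for the wrong groups as a matter of fact, or that the tables will wrongly show equal benefit. The documents support neither: few or no patients may be misplaced, no claim of equal effect is planned, and sampling error in subgroups of this size is large. The dilution figures rest on assumed rates and contamination, and the 75% figure on uniform timing among year-only recent diagnoses. The overall primary response rate does not change.

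**What to change.** **Rename.** Call the subgroup 'time since diagnosis, ≤6 vs >6 months' in Part A SAP 8.2.11, Table 14.1.2.1 and Table 14.2.10.4.x, and in Part B SAP 5.1.3, 5.4.1.1, Tables B.14.1.3.1 and B.14.2.1.5.x and Listing B.16.2.1.6. Use one named diagnosis date and one cut-off, stated in days, in both Parts. Reconcile the Table B.14.2.1.7.x footnote with 5.4.1.1 so that severity no longer turns on this label. List the departure from the protocol definition in the two changes sections.

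**Year-only dates.** Replace 01-JAN for this split. Take the earliest and latest possible dates, the latter no later than screening, and classify only if both fall on the same side of the cut-off; otherwise report unknown. Mid-year imputation is no better: under the model above it would date about 25% of recent year-only diagnoses after screening.

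**Clinical labels.** Use 'newly diagnosed' and 'relapsing' only for a subgroup built on documented prior induction and relapse, from medical history or source records. Include an 'unknown/other' category, which also takes patients whose earlier treatment never worked. Mark it post hoc where outcomes are already known; the last Part A patient completed on 20-Jun-2019.

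**Cost.** SAP and shell wording, some unclassified patients, and a few source queries if the treatment-based subgroup is wanted. Relabelling alone needs no new data.
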